#### 4.6 Unscheduled Visits

We do not anticipate any unscheduled visits, although unscheduled phone contact may occur with some participants (e.g., concern related to participant safety reported by caregiver or study interventionist; issue with actigraph).

**Participant safety concern.** Please see sections 7 and 8.4.1 for information about safety monitoring throughout this study.

**Actigraph issue.** If there are any issues with the actigraph device, families will be encouraged to contact a member of the study team by phone. Any issues will be handled primarily via phone, although an in-person visit may occur if the family must be provided with a replacement actigraph.

**Clinically significant mood, behavior, or safety concern.** At baseline, study participants will be provided with handout that lists resources obtaining mental health services, crisis intervention resources, and domestic violence/sexual abuse or assault/broad safety resources. This resource has been uploaded with this IRB submission. If a participant spontaneously reports significant concerns related to caregiver or child mood, behavior, or safety to a member of the study team, that team member will notify [name], who will then contact the family within 3 business days. During an unscheduled phone call, [name] will provide the family with appropriate community referrals for mental health services and direct the family to follow-up with their primary care clinician. [name] will also conduct a risk assessment over the phone. This risk assessment will contain questions about caregiver homicidal and suicidal ideation, and the presence of any homicide/suicide plan or intent, consistent with CHOP behavioral health risk assessment practices. Should there be an imminent safety risk, [name] will contact emergency services (911 or Pennsylvania mobile crisis services) for further suicide/homicide/risk assessment. All information obtained during the risk assessment will be used only for the purposes of determining appropriate follow-up care. Information about child safety concern or mandated reporting of any child abuse or neglect will be documented in the child's medical record, and will not be stored with study data, or used for any study-related data analysis. For caregiver risk assessment procedures, risk assessment will be documented in a Note to File coded by the participant ID and will be stored separately from the consent form and in a separate REDCap database used for tracking purposes only.

**Other follow-up issue.** If caregiver-child dyads that participated in the study contact the study team by phone to request follow-up, any issues will be handled via phone by Co-I [name], without an in-person visit.

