#### **4.3.2 Procedures for training Sleep Well! interventionists**

[name], a licensed psychologist who is also a Diplomat in Behavioral Sleep Medicine, will train and supervise all study interventionists, who are doctoral-level or post-doctoral level clinical psychology trainees at CHOP. [name] will provide each interventionist with approximately 8 hours of training prior to intervention. Interventionists will be trained to implement the treatment manual and attend to process variables, including establishing trust, listening actively, and re-directing tangential comments. All interventionists are mandated child abuse reporters and will be trained to identify and report child abuse and any other concerns related to participant safety. Consultation and peer supervision related to intervention delivery will occur weekly with [name] mentor, [name], Associate Director of the CHOP Sleep Center and Diplomat in Behavioral Sleep Medicine.

---

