#### **4.7 Subject Completion/Withdrawal**

Caregiver-child dyads may withdraw from the study at any time without prejudice to their care, education or employment. They may also be discontinued from the study at the discretion of the investigators for lack of adherence to the study and/or the emergence of exclusionary criteria. Children will be withdrawn from the study if any exclusionary criteria emerge during the study. Child well-being will be monitored by the interventionists and the caregiver throughout the study. If any adverse events occur that require clinical intervention during the course of study participation, a PI or co-investigator who is a licensed clinician will conduct a risk and safety assessment and make clinically appropriate referrals. If the investigators become aware of any serious, related adverse events after a participant completes or withdraws from the study, the event will be recorded in a separate, coded REDCap database used to track study attrition and any adverse events.

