The study members responsible for data collection and intervention will offer participants an opportunity to reflect on their experience (i.e., 'debrief') after they have completed the study procedures/intervention. In the rare event that a participant necessitates **psychological treatment due to adverse effects of study participation**, or a caregiver spontaneously discloses **low mood or other psychological concerns**, the study team member will contact the PI by phone, and the PI will speak with the participant, provide behavioral health resources, and screen for any suicide/homicide risk in a manner consistent with routine behavioral health practice at CHOP. Resources to mitigate risk (crisis numbers; referral resources) will be provided to participants verbally. Of note, at the baseline assessment, all participating families will be provided with a handout listing resources for obtaining mental health services, crisis services, and other safety-related services (domestic violence, sexual abuse and assault; see handout uploaded with this IRB submission).

All information obtained during any of the risk assessment procedures described above will be used only for the purposes of determining appropriate follow-up care. Information about mandated child abuse reporting or concerns for the child's safety will be documented in the child's medical record, and will not be stored with study data, or used for any study-related data analysis. For any caregiver-related risks (i.e., caregiver homicidal or suicidal risk), risk assessment information will be documented in a Note to File coded by the participant ID and will be stored separately from the consent form and in a separate REDCap database used for tracking purposes only.

There is also the risk related to the **potential loss of confidentiality**. All reasonable safeguards to secure the confidentiality of data will be taken by the study team (section 8.2).

---

The risk of breach of privacy and confidentiality are greatly reduced by using password-protected REDCap databases, storing data on secure CHOP computers and servers, and de-identification of data when applicable.

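### The only response time the protocol states for a reported mood, behavior or safety concern is 3 business days, with no shorter time when the disclosure suggests caregiver suicidal or homicidal ideation

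*Combined protocol and SAP*

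**What the plan says.** Section 4.6 (Unscheduled Visits) is triggered when a participant "spontaneously reports significant concerns related to caregiver or child mood, behavior, or safety to a member of the study team". That team member notifies one named responder, "who will then contact the family within 3 business days". On the call the responder gives community referrals, directs the family to primary care and assesses risk: "This risk assessment will contain questions about caregiver homicidal and suicidal ideation", along with plan and intent, in line with the hospital's behavioral health practice. If the risk is imminent, the responder "will contact emergency services (911 or Pennsylvania mobile crisis services) for further suicide/homicide/risk assessment".

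Section 8.4.2 (Risk Assessment) covers an overlapping event, in which a caregiver volunteers low mood or another psychological concern. There, "the study team member will contact the PI by phone, and the PI will speak with the participant", gives resources, and is to "screen for any suicide/homicide risk in a manner consistent with routine behavioral health practice at CHOP". No time is attached.

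Other sections bear on the same situation:
- Section 4.7: for adverse events that need clinical intervention, "a PI or co-investigator who is a licensed clinician will conduct a risk and safety assessment".
- Section 4.3.2: interventionists are trained to recognise and report child abuse and "any other concerns related to participant safety".
- Section 8.4.1: weekly safety meetings, telephone contact among the team while data are collected and the intervention is delivered, and licensed investigators.
- Sections 4.6 and 8.4.2: a handout of crisis and mental health resources at baseline. Section 8.4.2 adds that crisis numbers and referrals are given verbally.

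**The concern.** Section 4.6 has no severity tiers. A caregiver who mentions stress over bedtime tantrums and one who voices suicidal thoughts enter the same route with the same limit. Three business days is reasonable for a referral call. It is too long a ceiling for a first structured assessment of suicide or homicide risk, which is the gravest matter that paragraph names.

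Such disclosures are foreseeable. The background section links caregiver depression with child sleep problems and describes families under multiple stressors. Caregiver mood is measured at three assessments in both arms. The first person to hear a disclosure may be a research assistant who is reading questionnaire items aloud or taking diary entries by telephone (section 4.2), and control families do not meet an interventionist at all. For that person, section 4.6 states no duty beyond notifying the responder.

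At stake is participant safety. Under the stated rule, a wait of several days after voiced suicidal thoughts would be compliant with section 4.6.

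**Working it through.** The protocol gives no statistical figure here. The check is a comparison of sections and a conversion of the stated limit to calendar time.

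**Step 1: stated timing, section by section**

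| Section | Trigger | Who acts | Time stated |
|---|---|---|---|
| 4.6, contact and risk assessment | Volunteered significant mood, behavior or safety concern | Named responder | 3 business days |
| 4.6, emergency step | Imminent safety risk | Same responder | None |
| 8.4.2 | Volunteered low mood or psychological concern; treatment need due to participation | Team member phones PI; PI screens | None |
| 4.7 | Adverse event needing clinical intervention | Licensed PI or co-investigator | None |
| 4.3.2 | Participant safety concern | Interventionist identifies and reports | None |
| 8.4.1 | General safety oversight | Whole team | Weekly meetings and telephone contact; no response time |
| 7.1, 7.2 | Adverse events | Reporting to the IRB | No response time toward the family |

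One row carries a response time, and it makes no exception for suspected suicide or homicide risk. Where section 4.6 refers safety concerns elsewhere, it points to sections 7 and 8.4.1, and neither supplies one.

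**Step 2: how the emergency step relates to the call**

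The text does not make the emergency step conditional on the call. Its reference to further assessment suggests that it comes after an initial one. Either way, it is assigned to the responder and not to the person who receives the disclosure.

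**Step 3: the limit in calendar days**

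Input: 3 business days (section 4.6). Assumptions: a Monday-to-Friday working week, and notification on the day of disclosure, because section 4.6 sets no interval for that step. Formula: calendar days from the notification day to the third business day after it.

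| Notified | Limit falls on | Days, no holiday | Days, following Monday a holiday |
|---|---|---|---|
| Monday | Thursday | 3 | 3 |
| Tuesday | Friday | 3 | 3 |
| Wednesday | Monday | 5 | 6 |
| Thursday | Tuesday | 5 | 6 |
| Friday | Wednesday | 5 | 6 |
| Saturday | Wednesday | 4 | 5 |
| Sunday | Wednesday | 3 | 4 |

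The second column is for a week without a holiday. The ceiling is then 3 to 5 calendar days, and it is 5 for notification on Wednesday, Thursday or Friday. A Monday holiday raises the maximum to 6.

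The documents give no expected number of such disclosures, so no estimate of harm can be made.

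**The case against.** The strongest reply is that the protocol already has an urgent route. A team member phones the PI under section 8.4.2, staff are in telephone contact under section 8.4.1, imminent risk goes to emergency services with no 3-day allowance attached, and every family holds crisis contacts from baseline. Sections 4.6 and 8.4.2 both invoke the hospital's behavioral health practice, which may contain urgent timing. The limit is a maximum, licensed clinicians would very likely act sooner, and the study is classed as minimal risk.

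Most of this stands as mitigation. It does not supply a time. The crisis resources are passive, telephone contact is not a response standard, and the two sections cite institutional practice for the content or manner of the assessment, with no timing visible.

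Three stronger readings are tempting, and the documents do not support them:
- *Sections 4.6 and 8.4.2 contradict each other.* They do not. Section 8.4.2 states no time, so both can be followed together. Names are removed, so the responder in one may be the PI in the other.
- *Staff have no urgent route, or a caregiver in imminent danger must wait days.* The safeguards above rule that out. The gap is in stated timing and in who may start the emergency step.
- *Disclosed child abuse also waits 3 business days.* Sections 4.3.2 and 8.4.2 give that its own reporting route.

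**Conclusion.** The point holds as a gap in stated timing. For caregiver suicide or homicide risk, the protocol's only response time is a limit of 3 business days, equal to 3 to 5 calendar days without a holiday, and the emergency step rests with the responder alone. This goes beyond missing detail, because the rule as written permits the wait.

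The conclusion rests on the visible text and on the calendar assumptions stated with the conversion. If the unreproduced hospital practice sets a same-day standard, the remaining task is to state it in the protocol. Confidence is medium for that reason. The change is worth making for participant safety. It has no bearing on sample size, endpoints or analysis.

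**What to change.** Use the same wording in sections 4.6 and 8.4.2:
- Any disclosure that suggests suicidal or homicidal ideation, or imminent risk, is handed off by telephone at once to a licensed PI or co-investigator, who assesses risk the same day.
- If none can be reached, the team member who received the disclosure calls 911 or mobile crisis services.
- The 3-business-day limit stays for non-urgent referral calls.

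The cost is a text change in two sections and a staff briefing. The telephone hand-off, the licensed clinicians and the team's telephone contact are already in the plan; the same-day time and the fallback are new. The downside is that existing licensed investigators must be reachable the same day, including outside business hours, or the emergency fallback will be used.

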#### **4.7 Subject Completion/Withdrawal**

Caregiver-child dyads may withdraw from the study at any time without prejudice to their care, education or employment. They may also be discontinued from the study at the discretion of the investigators for lack of adherence to the study and/or the emergence of exclusionary criteria. Children will be withdrawn from the study if any exclusionary criteria emerge during the study. Child well-being will be monitored by the interventionists and the caregiver throughout the study. If any adverse events occur that require clinical intervention during the course of study participation, a PI or co-investigator who is a licensed clinician will conduct a risk and safety assessment and make clinically appropriate referrals. If the investigators become aware of any serious, related adverse events after a participant completes or withdraws from the study, the event will be recorded in a separate, coded REDCap database used to track study attrition and any adverse events.

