### **4.3 Study Treatment Phase**

#### **4.3.1 Intervention condition**

Sleep Well! will be provided over approximately 6-8 weeks, to allow for families to reschedule sessions as needed, and will include 3 sessions. Intervention sessions will typically last about an hour, but session length may vary. Content is delivered in a modular format based on family goals and the child's sleep concern (e.g., using electronics before bedtime; an inconsistent bedtime routine; etc.). To ensure high-quality care, intervention providers will receive regular supervision. Providers will also contact families by phone between sessions (3 times total) to (a) promote attendance, engagement, and implementation of Sleep Well! strategies, (b) assist in resolving barriers to treatment, and (c) guide families to community resources as needed. As noted above (3.1.2), text messages about the intervention will also be sent to families via Twilio and its integration with REDCap. For ethical reasons, families will be informed that they have the right not to participate in the study. If they choose not to participate, they will be referred to their pediatrician, who may provide the family with additional referrals to the CHOP Sleep Center or other behavioral health services, consistent with the current standard of care at CHOP.

Intervention sessions that occur in-person, via HIPAA-compliant video, or by telephone will be audio-recorded to monitor fidelity. Telephone check-in calls will not be audio-recorded. After each intervention session and intervention-related phone call, the interventionist will document which intervention contents were used using an intervention-specific fidelity checklist. The study interventionist will also document any feedback regarding the intervention as a method to assess intervention feasibility and usability. In addition, approximately 2 weeks into the intervention phase caregivers will complete a brief survey about their child's sleep electronically via REDCap (mid-point assessment).

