### 4.3.3 Control (enhanced usual care) condition

The enhanced usual care condition will occur for between 6 and 8 weeks. At randomization to this condition, participants will be provided with an evidence-based sleep guidelines for young children. These guidelines are summarized in the CHOP Parent Family Education manual and have been reviewed and approved by pediatric sleep experts (including study Co-I [name] and co-I [name]) and CHOP primary care physicians. Participants in this condition will also be able to consult with their primary care physician for management of child sleep. Consistent with usual care in the CHOP system, the primary care physician may manage the sleep concern or choose to make a referral to the CHOP sleep center or to other behavioral health services internal or external to the CHOP system. Of note, the CHOP Parent Family Education handouts provide contact information for the CHOP Sleep Center and direct readers to follow-up with their primary care provider for further guidance.

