## 5.4 Safety Evaluation

Participant safety will be monitored by adverse events throughout the study. Please see the Data Safety and Monitoring Plan (section 8.4.1) for further information.

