## 7 SAFETY MANAGEMENT

### 7.1 Clinical Adverse Events

Clinical adverse events (AEs) will be monitored throughout the study.

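### Adverse events reach the team through interventionists and unprompted reports, with no common question in both arms, so events during the intervention period are likely to be recorded more often in Sleep Well!

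*Combined protocol and SAP*

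**What the plan says.** Section 5.4 states: "Participant safety will be monitored by adverse events throughout the study". It refers on to section 8.4.1, which covers staff meetings, reporting to the IRB and a monitoring board that meets every 6 months, but not how families are asked. Section 7.1 is one sentence: "Clinical adverse events (AEs) will be monitored throughout the study".

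The means of detection appear elsewhere:

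- Section 4.7: "Child well-being will be monitored by the interventionists and the caregiver throughout the study".
- Section 4.6 gives, as an example of what may prompt an unscheduled call, a "concern related to participant safety reported by caregiver or study interventionist". Its procedure starts: "If a participant spontaneously reports significant concerns related to caregiver or child mood, behavior, or safety to a member of the study team".
- Section 8.4.2 adds an offer to reflect on the experience after study procedures, and acts on what is volunteered.

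Table 1 and the assessment lists in sections 4.2, 4.4 and 4.5 contain no adverse-event item for either arm. The record review in section 5.1.1 looks only for behavioral health or sleep services at CHOP.

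Contact differs by arm. Section 4.3.1 gives Sleep Well! families 3 sessions and 3 calls with an interventionist. Under section 4.3.3, control "participants will be provided with an evidence-based sleep guidelines for young children" and may consult their own physician. Each arm has one interview: at post-intervention for Sleep Well! (section 4.4) and at follow-up for controls (section 4.5).

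For the time after participation, section 4.7 provides for recording "any serious, related adverse events after a participant completes or withdraws from the study", if the investigators become aware of them.

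**The concern.** One of the two named watchers, the interventionist, exists in only one arm. The other, the caregiver, has to raise a problem unprompted, and Sleep Well! caregivers have six more conversations in which to do so. Detection during the intervention period therefore depends on the assigned arm.

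An excess of events in Sleep Well! could then reflect contact frequency, and a low control count could reflect silence. Anyone reading counts by arm, whether the monitoring board, readers of a paper or the designers of the larger trial that this one is meant to inform, could not separate the two. Events never asked about cannot be reliably recovered after data collection. Section 8.1.3 adds that the PI and coordinator who review adverse events are unblinded.

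A smaller point concerns section 4.7. After completion or withdrawal, seriousness and relatedness decide whether an event is recorded at all, when they could be attributes of a recorded event.

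**Working it through.** The documents give no adverse-event rate, disclosure probability or safety comparison, so there is no stated figure to reproduce. The following illustrates the possible size.

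**Contacts after randomization, from sections 4.3.1, 4.4 and 4.5**

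- Assessments done electronically: Sleep Well! 3 sessions + 3 calls + 1 interview = 7; control 1 interview.
- Assessments done in person: add the post-intervention and follow-up visits, giving 9 and 3.

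**Assumptions**

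- Each contact after an event brings it out with probability p, from 0.1 to 0.3.
- Events are uniform over weeks 0 to 20, with equal true rates.
- The six interventionist contacts are evenly spaced over weeks 2 to 8 (weeks 2, 3.2, 4.4, 5.6, 6.8 and 8). Post-intervention is at week 10 and follow-up at week 18. These times fit the ranges in section 3.1.
- Attendance is complete.

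**Formula.** With k contacts still to come after the event, D(k) = 1 − (1 − p)^k. Average D(k) over the event time, so that contacts before the event count for nothing.

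**Electronic assessments**

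Contacts still to come in Sleep Well!: 7 in weeks 0–2; then 6, 5, 4, 3 and 2 in successive 1.2-week steps to week 8; 1 in weeks 8–10; none afterwards. Control: 1 until week 18.

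- p = 0.1, Sleep Well!: [2 × 0.522 + 1.2 × (0.469 + 0.410 + 0.344 + 0.271 + 0.190) + 2 × 0.1] / 20 = 3.26 / 20 = 16%. Control: 18 × 0.1 / 20 = 9%. Ratio 1.8.
- p = 0.3, Sleep Well!: [2 × 0.918 + 1.2 × (0.882 + 0.832 + 0.760 + 0.657 + 0.510) + 2 × 0.3] / 20 = 6.80 / 20 = 34%. Control: 18 × 0.3 / 20 = 27%. Ratio 1.3.

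**In-person assessments**

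Sleep Well!: 9 in weeks 0–2; then 8, 7, 6, 5 and 4; 3 in weeks 8–10; 1 in weeks 10–18. Control: 3 in weeks 0–10; 2 in weeks 10–18.

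- p = 0.1, Sleep Well!: [2 × 0.613 + 1.2 × (0.570 + 0.522 + 0.469 + 0.410 + 0.344) + 2 × 0.271 + 8 × 0.1] / 20 = 5.34 / 20 = 27%. Control: [10 × 0.271 + 8 × 0.19] / 20 = 21%. Ratio 1.3.
- p = 0.3, Sleep Well!: [2 × 0.960 + 1.2 × (0.942 + 0.918 + 0.882 + 0.832 + 0.760) + 2 × 0.657 + 8 × 0.3] / 20 = 10.83 / 20 = 54%. Control: [10 × 0.657 + 8 × 0.51] / 20 = 53%. Ratio 1.0.

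**Events in weeks 0–8 only** (first two terms of each Sleep Well! sum, divided by 8)

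- Electronic: 38% against 10% at p = 0.1 (ratio 3.8); 78% against 30% at p = 0.3 (ratio 2.6).
- In person: 50% against 27% (ratio 1.8); 89% against 66% (ratio 1.4).

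After week 10 the model favors control slightly, by one contact, because the control interview comes later. That is why the whole-study ratio is much smaller than the early one.

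**The case against.** The strongest case against is that no planned result is affected. Sections 6.1 to 6.4 contain no between-arm adverse-event analysis. Section 7.2 sends notable non-serious events to the IRB as a summary. Section 8.4.1 does not say that the board sees counts by arm. Risk is rated no greater than minimal, and unequal therapist contact is inherent in comparing therapy with usual care. All of this stands, and it keeps the point modest.

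Controls are also not unobserved. Both arms complete the same child sleep, child behavior, caregiver mood, caregiver sleep and stressor measures at post-intervention and follow-up, have the same limited record review and are offered the debrief. Section 4.2 lists randomization before the 7-day diary and actigraphy, so controls have some study contact just afterwards. These measures would show deterioration equally in both arms, but none is linked to adverse-event recording, and Sleep Well! families have them too.

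A reader might infer four stronger things that the documents do not support:

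- *That recording will differ several-fold over the whole study.* Applying D(k) to all contacts gives ratios of 3.1 to 5.2 (electronic) or 1.5 to 2.3 (in person), but it credits contacts that took place before the event.
- *That harm behind a withdrawal is lost.* The serious-and-related condition covers events learned of after completion or withdrawal. An event that leads to withdrawal arises during participation, where section 7.1 applies, and section 4.8 attempts contact with all who withdraw in the intervention phase.
- *That the 15% attrition in section 6.5 counts the dyads under that condition.* It is expected attrition at follow-up, not a withdrawal rate.
- *That the post-withdrawal rule makes the net direction of bias unknowable.* An opposing bias from that source would need more withdrawals in Sleep Well! than in control, and no section says so.

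**Conclusion.** The concern holds as a modest weakness in how harms are ascertained. Detection rests on interventionists and unprompted reports, nothing asks both arms the same question, and Sleep Well! has six extra contacts. At equal true rates, events in the intervention period are expected to be recorded more often there. This is an expectation: with few events, chance could hide or reverse it.

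The size is not known. Under the assumptions above, the detection ratio over the study is roughly 1.0 to 1.8, and larger for early events. It depends on the disclosure chance, the timing of events and the mode of assessment, and missed sessions would shrink it. The consequence falls on any counts presented by arm, not on a planned test.

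**What to change.** 1. Add the same brief adverse-event items, in the same words, to the REDCap questionnaires at post-intervention and follow-up in both arms, and to the early-termination contact in section 4.8. Add a row to Table 1.
2. Base any by-arm summary on these solicited events. Tabulate events volunteered to interventionists separately.
3. In section 4.7, record events learned of within the planned participation window (up to 24 weeks in section 3.3.1), with seriousness and relatedness as coded fields and not as conditions for entry.

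Because section 4.6 is written for spontaneous reports, the protocol should also say how a solicited answer enters that process.

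Solicited detection is then equal by design; volunteered reports remain unequal, hence the separate table. The cost is a few items at two existing assessments, about 2 minutes of caregiver time (assumed), more minor events to log and review, and small wording changes. No new visits or staff are needed.
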